Feasibility of recruitment: In 2019, 987 patients with OUD and CP diagnoses of back pain, arthritis, or neuropathy were hospitalized at Montefiore. Co-morbidities that would be exclusions for this RCT were: BUP treatment (7%), methadone treatment (31%), severe alcohol use disorder (8%), and severe benzodiazepine use disorder (2%). Removing patients with ≥ 1 exclusion leaves 640 potential participants. In a prior RCT of BUP treatment for hospitalized patients, 21% of eligible patients were enrolled.¹⁸ Using a more conservative estimate of enrolling 14% of eligible patients, enrolling 270 participants in 3 years will be feasible (640 eligible/year x 14% enrollment rate x 3 years = 270 participants).

D.2.5 Screening and Randomization: Initial screening and consent: Participants will be screened for eligibility and exclusion criteria by a trained research coordinator using a brief questionnaire. Participants will be informed of study procedures, risks and benefits of study participation, tested for their understanding, and they will provide written consent. During enrollment, female participants will have urine pregnancy tests.

Randomization will be unblinded, stratified, and blocked, with a 1:1 ratio across the two arms. To ensure balanced distribution between arms, we will stratify by OUD severity (misuse/mild vs. moderate/severe), heroin use (past 30 days, yes vs. no), and mood disorders (yes vs. no). We will randomize in blocks of 4-8 to ensure comparison groups of equal size. To ensure concealment of allocation, a centrally-located data manager will generate allocation sequences (with SAS Proc Plan) and store sequences in a password-protected file.

D.2.6 Participant tracking: We will use procedures that we have developed to retain people who use drugs in previous research, in which we have had an 84% retention rate over 6-month-follow-up.¹¹⁰ Participants will complete locator forms at enrollment and update them at all research visits. Information will include: 1) participants' addresses, phone numbers, and social security numbers; 2) contact information of family or friends; 3) contact information of participants' community-based organizations and case managers; and 4) participants' "hang out" locations.

Table E-2. Microdosing Initiation Dosing Schedule

Day	Microdosing			Standard Induction		
	Full agonist	BUP	Daily Total	Full agonist	BUP	Daily Total
1	Full dose	0.5 mg q12	1 mg	STOP	--	--
2	Full dose	1 mg q8	3 mg	--	2 mg q4 h	8 mg

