Intervention fidelity: Study clinicians will be trained in the study protocol for microdosing and TAU and follow a check-list for induction procedures. All BUP doses administered will be recorded in medical records.

Follow-up BUP treatment: Participants will be discharged with 1 week of BUP and scheduled for clinical visits at Montefiore within 1 week. During clinical visits, participants will be assessed for BUP adherence, illicit opioid use, and opioid craving. All BUP prescriptions will be buprenorphine-naloxone film or tablet formulations.

Maintenance dosing: For both arms, the target BUP dose will be 16 mg daily at discharge, consistent with the mean BUP dose for patients treated at Montefiore and standard clinical dosing goals for OUD.¹¹⁵ As per standard procedures, clinical visits will occur weekly during the first month. BUP dosage may be increased if needed (based on opioid use or uncontrolled pain).

Psychosocial counseling and support: At clinical visits, clinicians will provide 15 minutes of standardized counseling directed toward medical management.¹¹⁶ Counseling will include discussion of current substance use, BUP adherence, and psychoeducation about avoiding relapse. **End of study:** At 6-months, all participants will have the option to continue clinical care at a Montefiore clinic, including those without insurance.

D.2.8 Assessment Visits: A research assistant (RA) will meet with all participants at baseline, 1 week, and 1, 3 and 6 months (see Table E-3). Research visits will occur in the hospital or at a Montefiore clinic, and participants will receive \$50 compensation at visits for the week 1, month 1 and month 3 visits and they will

Construct	Measure	Assessment period				
		0	1w	1m	3m	6m
Opioid Outcome Measures for Aim 1						
BUP uptake	BUP medication administration, prescriptions		X			
BUP retention	BUP prescriptions			X	X	X
Illicit opioid use	Addiction Severity Illness (ASI), urine drug test	X	X	X	X	X
Pain Outcome Measures for Aim 1						
Pain intensity	BPI pain severity subscale	X	X	X	X	X
Pain interference	BPI pain interference subscale	X	X	X	X	X
Quality of life	PROMIS-Preference (PROP-Pr) Scoring System	X		X	X	X
Physical functioning	PROMIS Physical Function short form	X	X	X	X	X
Additional Mediators/Moderators and Covariates						
Sociodemographics	Demographics questionnaire	X				
Opioid withdrawal	Clinic Opioid Withdrawal Scale (COWS)	X	X			
Opioid craving	Medication Craving Scale	X		X	X	X

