Secondary OUD outcomes include illicit opioid use and BUP retention. **Illicit opioid use** will be examined as the number of days of illicit opioid use (defined as self-reported use of heroin, fentanyl, or non-prescribed opioid analgesics) in the prior 30 days based on the Addiction Severity Index (continuous).¹¹⁹ Because urine drug testing (UDT) only captures opioid use in the prior 24-72 hours, it is a less sensitive measure of substance use over time; however, UDT results will be a secondary outcome measure. **BUP retention** will be

Table E-4. Ecological Momentary Assessment (EMA) Measures

Construct	Measure
EMA opioid- and pain-related symptoms	
Opioid withdrawal	Subjective Opioid Withdrawal Scale (SOWS)
Opioid craving	Visual analog scale
Pain intensity	Adapted BPI pain severity subscale
Anxiety	Generalized Anxiety Disorder-7 (GAD-7)
Exploratory EMA outcomes	
Illicit opioid use	Self-report
BUP dose	Self-report
Pain treatment	Self-report

*All measures will occur at bursts 1 & 2 weeks, and 1, 2, & 3 months

defined as having a BUP prescription written the following number of days after baseline: 30-60 days (1-month retention); 90-120 days (3-month retention); and 180-210 days (6-month retention). To be retained at 3 and 6-months, participants will be required to have been retained at previous time points.⁴⁶ All OUD outcomes are consistent with elements of the Opioid Use Disorder Cascade of Care.¹²⁰

Secondary pain outcomes include pain intensity, pain interference, and quality of life. *Pain intensity* will be measured using the Brief Pain Inventory (BPI).¹²¹ We will use the mean of 4 items that assess pain intensity over the past 24 hours on a scale of 1-10 (1=minimal pain, 10=intense pain). We will use the mean of these 4 items. *Pain interference* will be measured using the pain interference scale from the BPI, which is a 7-item instrument measuring the impact of pain on daily activities and physical functioning. It is rated on a scale of 1-10 (1=minimal interference, 10=high interference). We will use the mean of these 7 items. *Quality of life* will be measured using the PROMIS-Preference Scoring System (PROP-Pr), which is described in detail as part of the cost-effectiveness analyses below (see D.4.1).¹²²⁻¹²⁴ In our main analyses, we will examine changes from baseline to 3 months for all pain outcomes; in additional analyses, we will examine sustainability at 6 months.

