Other covariates: We will include covariates that may be associated with study outcomes including: sociodemographic characteristics (age, race/ethnicity, sex, employment, housing, insurance), opioid withdrawal and craving,^{111,125} adjunctive withdrawal medications (e.g., clonidine, loperamide), pain treatments including medications (e.g., NSAIDs, gabapentin) and other forms of treatment (e.g., physical therapy, steroid injections, surgery), mood symptoms (anxiety and depression),¹²⁶⁻¹²⁸ and prior OUD treatment. We will also include holistic outcome measures developed by the IMPOWR Coordination and Dissemination Center with people with lived experience (RFA-DA-21-029) and collaborate with the IMPOWR-ME Stakeholder Board to ensure we include other measures important to them.

D.2.11 Analytic plan Aims 1 and 2: Main analyses will be completed using an intention-to-treat approach.

[figure not shown]
Preliminary analyses. We will first review and summarize data using descriptive summaries and graphical analyses to ensure that values are within appropriate ranges, to check for outliers and abnormal values, and to verify that the distributions of measures meet the assumptions of the statistical tests that are planned as described below. We will also explore whether the microdosing and TAU groups are equivalent on potential confounding variables (age, sex, race/ethnicity, baseline substance use, and mood symptoms).

Missing data. For missing data, we will use multivariate multiple imputation using the fully conditional specification method.¹²⁹ We will repeat imputations five times, and then we will compare statistical results using datasets that include imputed values and the dataset that drops missing values. This will guide interpretation of our assessment of the impact of missing data, as well as, our interpretation of overall results.

Aim 1: To test the effectiveness of microdosing (vs. TAU) on OUD outcomes.

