H₁: *The microdosing arm (vs. TAU) will have better BUP treatment uptake and retention, and less illicit opioid use.* Our primary analysis will be a logistic regression comparing the proportion of participants in each study arm who meet our definition of BUP uptake (see D.2.10). Secondary analyses will examine BUP retention and illicit opioid use as secondary outcomes. We will use a mixed effects logistic regression model to examine BUP retention at 1, 3, and 6 months and a mixed effects linear regression model to examine number of days of illicit opioid use (over 30 days) at 1, 3, and 6 months. Study arm will be considered a fixed effect, and participant and time (months) will be considered random effects. Additional analyses will include key variables mentioned above as covariates and potential confounders if they differ by study arm.

H₂: *Improvements in H₁ will be mediated by opioid- and pain-related symptoms.* Based on the model

described in **Figure E-3**, we will use structural equation modeling to determine whether improvements in OUD outcomes are due to improvements in opioid- and pain-related symptoms. We will use EMA data (5 random reports per day) and data from in-person visits at baseline, 1 week, 1, 3, and 6 months. For example, when the dependent variable is BUP uptake, we will calculate the standardized total effect from the intervention (BUP microdosing) to BUP uptake, as well as the standardized mediational (i.e., indirect) effect of opioid- and pain-related symptoms (e.g., withdrawal). The mediational effect is calculated as the product of the effect from intervention to the mediator, and the effect from the mediator to the outcome. To account for the influence of the baseline measures (e.g., sociodemographic characteristics) on the outcome and the mediator, we will use a partial correlation matrix as the input matrix. This will be created by statistically parsing out the effects of the baseline measures cited above on the mediator and the outcome variable. Our proposed model will be estimated using Mplus.¹³⁰ Overall model fit will be assessed by: (1) the root mean

[figure not shown]

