effect of opioid- and pain-related symptoms (e.g., withdrawal). The mediational effect is calculated as the product of the effect from intervention to the mediator, and the effect from the mediator to the outcome. To account for the influence of the baseline measures (e.g., sociodemographic characteristics) on the outcome and the mediator, we will use a partial correlation matrix as the input matrix. This will be created by statistically parsing out the effects of the baseline measures cited above on the mediator and the outcome variable. Our proposed model will be estimated using Mplus.¹³⁰ Overall model fit will be assessed by: (1) the root mean

square error of approximation (RMSEA), (2) Bentler's comparative fit index (CFI),¹³¹ and (3) the standardized root mean square residual (SRMR). To account for non-normal distribution of the model variables (e.g., BUP uptake), we will use Mplus's maximum likelihood with robust standard errors (MLR) as the estimator.

Aim 2: To test the effectiveness of microdosing (vs. TAU) on pain outcomes.

H₃: The microdosing arm (vs. TAU) will have less pain intensity and interference, and improved quality of life. We will use separate mixed effects linear regression models to compare each pain outcome from baseline to 3 months. Main analyses will use data from in-person visits at baseline, 1 week, 1 and 3 months. Study arm will be considered a fixed effect, and participant and time will be considered random effects. In additional analyses, we will include key variables mentioned above as covariates and potential confounders if they differ by study arm. We will also examine sustainability of outcomes at 6 months.

H₄: Improvements in H₃ will be mediated by OUD outcomes. Based on the model described in **Figure E-4**

and similar to the analyses for H2 (see above), we will use structural equation modeling to determine whether improvements in pain outcomes are due to improvements in OUD outcomes. For example, when the dependent variable is pain intensity, we will calculate the standardized total effect from the intervention (BUP microdosing) to pain reduction at 3 months, as well as the standardized mediational (i.e., indirect) effect of BUP uptake, BUP retention, and illicit opioid use. For these analyses, our primary mediator is BUP retention. We will use both the EMA data (5 random reports per day) and data from in-person visits at baseline, 1 week, 1 and 3 months.

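### The main H1 illicit-use model omits baseline days of use, which the trial already collects, and so loses precision on a secondary outcome

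*Combined protocol and SAP*

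**What the plan says.** The key-outcomes section (headed E.2.10) defines illicit opioid use as a secondary OUD outcome: the self-reported number of days of use in the past 30, from the ASI, treated as continuous. The illicit-use row of Table E-3, "Addiction Severity Illness (ASI), urine drug test", is marked at baseline, 1 week, and 1, 3 and 6 months.

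For H1, section D.2.11 specifies a "mixed effects linear regression model to examine number of days of illicit opioid use (over 30 days) at 1, 3, and 6 months". The model terms are: "Study arm will be considered a fixed effect, and participant and time (months) will be considered random effects". On further variables it says: "Additional analyses will include key variables mentioned above as covariates and potential confounders if they differ by study arm".

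Baseline substance use is mentioned in two other places. The preliminary analyses in D.2.11 list the potential confounders to be compared between arms: "age, sex, race/ethnicity, baseline substance use, and mood symptoms". The covariate block of Table E-3 also has a substance-use row that names the ASI and is marked at baseline.

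The H3 pain models in the same section are set up differently: "Main analyses will use data from in-person visits at baseline, 1 week, 1 and 3 months".

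**The concern.** The baseline value of an outcome is a natural covariate for its follow-up values, and here it is collected anyway. The main H1 illicit-use model does not use it. The pain models do bring in baseline data, and the plan gives no reason for the difference.

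Eligibility (D.2.3) admits people who use heroin, and also people who overuse or run out early of their own prescription. The outcome counts heroin, fentanyl and non-prescribed analgesics. Participants may therefore enter with very different numbers of illicit-use days. Whatever part of that spread persists into follow-up stays in the residual variance of the arm comparison.

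What is at stake is the width of the confidence interval for one of the three components of H1 (uptake, retention and illicit use). No power figure is given for this outcome, so the plan shows no margin that would make the loss harmless.

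**Working it through.** **1. Reproduce the plan's own figure.** Section D.2.12 gives no SD or detectable difference for days of use. The nearest figure is for pain: d = 0.34 with 135 per arm and 80% power. Alpha is not stated; two-sided 0.05 is assumed.

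Detectable difference = (1.960 + 0.842) × √(2/135) = 0.341 SD. With an SD of change of 1.8 this is 0.614 points, and 0.614/7.3 = 8.4%. Both of the plan's figures (0.34 and 8.4%) are reproduced, so 0.341 SD is a fair unadjusted reference for a continuous outcome at one visit.

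**2. Add the baseline covariate, single visit.** Let ρ be the correlation between baseline and follow-up days. It is an assumption, because the documents do not give it. Adjustment multiplies the residual variance by 1 − ρ², the detectable difference by √(1 − ρ²) and the equivalent sample by 1/(1 − ρ²).

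| ρ | Variance removed | Factor on detectable difference | Detectable difference (SD) | Power at d = 0.34 | Equivalent n per arm |
|---|---|---|---|---|---|
| none | – | 1 | 0.341 | 80% | 135 |
| 0.2 | 4% | 0.980 | 0.334 | 81% | 141 |
| 0.3 | 9% | 0.954 | 0.325 | 83% | 148 |
| 0.5 | 25% | 0.866 | 0.295 | 90% | 180 |
| 0.6 | 36% | 0.800 | 0.273 | 94% | 211 |

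At the 84% retention of the group's earlier research (D.2.6), about 113 per arm remain. The unadjusted value is then 0.373 SD, and the adjusted values are 0.365, 0.356, 0.323 and 0.298.

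**3. Three visits together.** The H1 model pools three visits. With an assumed correlation f between follow-up visits, the variance of a participant's mean is (1 + 2f)/3 without baseline and (1 + 2f)/3 − ρ² with it. For f = 0.6:

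- Unadjusted: (1 + 1.2)/3 = 0.733, so 0.341 × √0.733 = 0.292 SD.
- ρ = 0.2: 0.733 − 0.04 = 0.693, giving 0.284 SD (3% lower).
- ρ = 0.3: 0.733 − 0.09 = 0.643, giving 0.274 SD (6% lower).
- ρ = 0.5: 0.733 − 0.25 = 0.483, giving 0.237 SD (19% lower).

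Under this assumption the single-visit figures do not exaggerate the gain for the repeated-measures model.

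**4. Does the conditional rule recover the gain?** Trials with 135 per arm and d = 0.34 were simulated, 6,000 per setting. The plan sets no threshold for a difference between arms, so p < 0.05 on baseline was assumed. The simulation is generous to the plan, because it lets the adjusted result replace the main one whenever the rule fires.

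| ρ | Never adjust | Adjust only if baseline differs | Always adjust |
|---|---|---|---|
| 0.3 | 79% | 79% | 82% |
| 0.5 | 79% | 80% | 90% |
| 0.7 | 80% | 81% | 97% |

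The rule fires in about 5% of trials, which is what randomization implies. With no true effect it did not reject too often; at ρ = 0.7 it rejected in 3.6% of trials.

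**The case against.** **The plan already names baseline substance use as a covariate.** A reader might infer that it appears only in the balance check. It does not: the covariate block of Table E-3 lists it, and the covariate paragraph before D.2.11 is worded as an open list. The H1 sentence can also be read so that the condition on arm differences limits only the confounders. An unconditional adjusted analysis may then already be intended. This stands as a reading, but that analysis would still be an additional one. On either reading the main model omits baseline days.

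**Imbalance is already controlled.** A reader might infer that the arm comparison is biased, or exposed to serious imbalance. Randomization makes the unadjusted estimate unbiased, and its standard error reflects chance imbalance. D.2.5 also stratifies on past-30-day heroin use and OUD severity, which limits the contrast between heroin users and people misusing prescriptions. This objection stands. The stratifiers do not record the number of days, though, and they are not named as model terms.

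**The gain may be small.** The documents give no SD, distribution or correlation for days of use. Nothing in them shows that this outcome is unusually variable or that its baseline is the best predictor available. All participants are currently taking opioids, and the recruitment lists target diagnosed OUD. Baseline days may therefore cluster near 30, which would lower ρ. At ρ = 0.2 the detectable difference moves only from 0.341 to 0.334 SD. This stands, and it is why the range starts at 0.2.

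**Conclusion.** The point holds as a matter of efficiency and pre-specification on one secondary outcome. The main H1 illicit-use model leaves out a baseline value that the trial collects, and the route left open for it yields almost none of the available precision.

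The size rests on an assumed ρ. For 0.2 to 0.6, adjustment removes 4% to 36% of the single-visit variance and lowers the detectable difference by 2% to 20%, equivalent to about 4% to 56% more participants. The calculation assumes a roughly linear relation between baseline and follow-up days.

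The point does not touch the primary outcome, BUP uptake, and it implies neither bias nor inflated type I error. A reader might also extend it to the quality-of-life model in the cost-effectiveness section (D.4). The documents do not support that: HRQoL is modelled there at each assessment point, so its baseline value may already be a response.

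**What to change.** In D.2.11, H1, state that the main illicit-use model includes baseline ASI days of illicit opioid use as a fixed covariate, whatever the observed balance, and that the condition on arm differences does not apply to this variable. The unadjusted model can be kept as a sensitivity analysis.

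The cost is one sentence in the analysis plan and one degree of freedom. No visit, instrument or participant burden is added. If ρ proves low, little is gained and essentially nothing is lost.

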3	Full dose	2 mg q8	6 mg	--	8 mg BID	16 mg
4	Full dose	4 mg q8	12 mg	--	8 mg BID	16 mg

D.2.7 Clinical Protocols: Microdosing**(Experimental arm):**

Participants randomized to microdosing will start low-dose BUP while continuing a full opioid agonist according to a 4-day protocol (see **Figure E-2 & Table E-2**). Participants will be assessed for opioid withdrawal using the clinical opioid withdrawal scale (COWS) before the first BUP dose and 30 minutes after each administered dose while hospitalized.¹¹¹ A full opioid agonist will be continued until day 5 of the protocol.^{112,113} If patients are planned for discharge before completing

microdosing, they will receive at the time of discharge pre-packed medication clearly marked with the timing for each dose, instructions on how to take the medication and when to stop full agonist opioids. Opioid withdrawal will be assessed with the Subjective Opioid Withdrawal Scale (SOWS) via telephone.

Rationale for 5-day protocol: Published microdosing protocols range from 3 to 7 days or more. From 2012-2016, the mean length of stay for patients at Montefiore Medical Center with an opioid positive urine drug test was 7.62 days (95% CI: 7.44-7.80). Some evidence suggests that rapid titration to maintenance BUP treatment dosages prevents drop-out,¹¹⁴ but rapid titration could increase precipitated withdrawal risk, therefore, we developed our protocol in the middle of the published range.

TAU (Control arm): Participants randomized to TAU will receive a standard BUP induction following clinical guidelines. Full opioid agonists will be stopped and a clinician will assess for withdrawal using the COWS scale. If participants have a COWS score of ≥ 8 they will be eligible to receive a 2 mg BUP dose. Participants will be reassessed for withdrawal 30 minutes after receiving their first BUP dose.

Withdrawal management: Participants with COWS score increases of $\geq 50\%$ or an absolute increase of 4 or more will be considered to have precipitated withdrawal. If this occurs, induction will be postponed to the following day. Clinicians can administer non-opioid adjunctive medications (i.e., clonidine, loperamide) during induction based on hospital protocols. Medication use will be considered a covariate in analyses with withdrawal symptoms as an outcome.

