Pain treatments	Prescriptions, pain-related visits/procedures	X		X	X	X
Mood symptoms	Patient Health Questionnaire (PHQ-9) Generalized Anxiety Disorder-7 (GAD-7)	X		X	X	X
Substance use	PROMIS alcohol use, ASI, urine drug test	X	X	X	X	X
Prior OUD treatment	NIDA JCOIN harmonized questionnaire	X				
**Additional measures will be included as required by the RFA, IMPOWR Coordination and Dissemination Center, and IMPOWR-ME Stakeholder Board.						

receive \$100 for the baseline and month 6 visits. Questionnaires and urine drug tests will be completed at each study visit. Additionally, data will be collected using EMA in the hospital during induction and in between assessment visits (see below). To limit participant burden, EMA data will be collected only during induction over 2 weeks and then in three 1-week bursts during follow-up.

D.2.9 Data Sources and Measures for Aims 1 and 2 are presented in **Tables E-3 and E-4**.

Questionnaires: Questionnaires will be administered in English or Spanish using REDCap, a well-established, HIPAA-compliant, web-based surveying platform and database that allows flexible instrument design, ease of contacting potential respondents, and reliable data collection and storage with error control. Additionally, items can be self- or interviewer-administered. Our team has transitioned to online evaluations due to the COVID-19 pandemic and all instruments can be filled out online. Therefore, questionnaires can be administered at a Montefiore clinical site or virtually.

Medical Records: We will abstract medical record data from the electronic health record (EHR), including administration of BUP during hospitalizations, BUP prescriptions and outpatient BUP visits. We will also abstract adjunctive medications administered in the hospital for managing opioid withdrawal and pain, and any pain medications prescribed in the outpatient setting during follow-up. We will abstract other pain-focused visits or interventions during the follow-up period (e.g., physical therapy).

Urine Drug Testing will occur at each study visit using enzyme-multiplied immunoassay (EIA) technique for opiates, oxycodone, fentanyl, methadone, BUP, amphetamines, benzodiazepines, cocaine, and cannabinoids, and urine creatinine concentration to ensure validity.

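### The H1 and H3 models do not name the three stratification factors, and withdrawal comparisons are to be adjusted for medication given after randomisation

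*Combined protocol and SAP*

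**What the plan says.** Section D.2.5 (Screening and Randomization) uses 1:1 allocation in blocks of 4 to 8, and "we will stratify by OUD severity (misuse/mild vs. moderate/severe), heroin use (past 30 days, yes vs. no), and mood disorders (yes vs. no").

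Section D.2.11 sets out the models. For the primary outcome: "Our primary analysis will be a logistic regression comparing the proportion of participants in each study arm who meet our definition of BUP uptake". For the secondary H1 models: "Study arm will be considered a fixed effect, and participant and time (months) will be considered random effects". The H3 pain models have the same structure. Covariates appear only in supplementary work, for H1 as "Additional analyses will include key variables mentioned above as covariates and potential confounders if they differ by study arm" and for H3 as "In additional analyses, we will include key variables mentioned above as covariates and potential confounders if they differ by study arm".

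Two lists could be the variables meant. The preliminary-analyses paragraph of D.2.11 gives age, sex, race/ethnicity, baseline substance use and mood symptoms. The longer list of other covariates, at the end of the key-outcomes section (numbered E.2.10), adds withdrawal, craving, adjunctive withdrawal medication and pain treatments.

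Section D.2.7 (Withdrawal management) says "Clinicians can administer non-opioid adjunctive medications (i.e., clonidine, loperamide) during induction based on hospital protocols" and then "Medication use will be considered a covariate in analyses with withdrawal symptoms as an outcome". Section D.2.9 (Medical Records) gives the purpose of these drugs: the team will abstract "adjunctive medications administered in the hospital for managing opioid withdrawal and pain, and any pain medications prescribed in the outpatient setting during follow-up". Exploratory analysis E1 in D.2.11 compares withdrawal by arm using arm, then time, then their interaction. It lists no medication term.

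**The concern.** There are three linked gaps.

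- **Strata.** When allocation is balanced within strata and the analysis ignores them, the standard error is too large if the strata predict outcome. The test becomes conservative, and precision that the design has already paid for goes unused.
- **Medication.** Adjunctive drugs given during induction come after randomisation and are prompted by the symptom being compared. Holding their use constant removes part of the arm difference and also compares patients selected on their symptoms. The adjusted contrast is not the effect of assignment. Avoiding withdrawal is the trial's proposed mechanism, so the comparison matters even though it is exploratory.
- **Adjusted H1 and H3 analyses.** The text does not say which list is meant, or which visit's value is used for items measured more than once. Part of the covariate set depends on observed arm differences. If the longer list is meant, post-randomisation values could enter models that are supposed to estimate the arm effect.

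**Working it through.** **The plan's own figure.** Section D.2.12 gives 61% vs 24% uptake, 80% power and 27 per arm. I assume two-sided 0.05, with pooled variance and no continuity correction. The mean proportion is 0.425:

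n = [1.96 × √(2 × 0.425 × 0.575) + 0.842 × √(0.61 × 0.39 + 0.24 × 0.76)]² / 0.37² = (1.370 + 0.546)² / 0.1369 ≈ 26.8, so 27.

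The figure reproduces. At the planned 135 per arm, power for 61% vs 24% is essentially 100%. The point changes no sample-size figure.

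**Strata, approximate size of the arm-only test.** If the strata explain a share R² of outcome variance and are balanced, the true two-sided size is 2 × [1 − Φ(1.96 / √(1 − R²))]. This gives 4.8% at R² = 0.02, 4.4% at 0.05, 3.9% at 0.10 and 2.8% at 0.20.

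**Strata, simulation.** The set-up was 270 patients, 8 strata, permuted blocks of 4, 6 or 8, logistic regression with a Wald test, and 20,000 replicates per cell (Monte Carlo SE about 0.3 points for power and 0.15 for type I error). Assumptions, none of them in the documents: three independent factors at 50% prevalence, equal odds ratios, and uptake of 61% vs 44%. The 44% was chosen because 135 per arm then has about 80% power.

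| Factor OR | Power, arm only | Power, with strata | Type I error, arm only |
|---|---|---|---|
| 1 | 79.5% | 80.2% | 4.5% |
| 1.5 | 79.7% | 81.7% | 4.6% |
| 2 | 80.3% | 83.4% | 3.8% |
| 3 | 81.7% | 87.1% | 2.9% |

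- The gap at OR 1 (0.8 points before rounding) is not recovered precision. Net of it, the gain is 2.0 − 0.8 = 1.2, 3.1 − 0.8 = 2.3 and 5.4 − 0.8 = 4.6 points at OR 1.5, 2 and 3.
- With only one prognostic factor, the net gain is (81.6 − 79.8) − 0.8 = 1.0 at OR 2 and (83.1 − 80.0) − 0.8 = 2.3 at OR 3.
- An unstratified Wald test at 135 per arm and 52.5% uptake has an exact size of 4.5%. Conservatism due to the strata therefore shows only at OR 2 to 3. With the strata in the model, type I error is 4.9 to 5.3%.
- At 61% vs 24%, power is about 100% with or without the strata.
- In a separate simulation with the same blocking, none of the three factors was ever selected by a test of arm difference at p < 0.05.
- Adding the strata makes the odds ratio conditional: 2.14 at factor OR 2 and 2.33 at OR 3, against 2.00 unadjusted.

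**Medication covariate.** Assumptions: a 0.5 SD arm difference before any drug effect, 40% medicated overall, and a correlation of 0.3, 0.5 or 0.7 between withdrawal and the tendency to be medicated. The identity is adjusted difference = unadjusted difference − γ × (P₁ − P₀). Here γ is the medication coefficient given arm, and P₁ and P₀ are the proportions medicated on microdosing and TAU.

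- Correlation 0.7, no drug effect: −0.50 − 1.13 × (0.333 − 0.467) = −0.35, about 30% smaller.
- Correlation 0.3, 1.0 SD drug effect: −0.443 − (−0.517) × (0.371 − 0.429) = −0.473, about 7% larger.

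Change in the arm difference across the grid:

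| Drug effect | Corr. 0.3 | Corr. 0.5 | Corr. 0.7 |
|---|---|---|---|
| 0 | −5.6% | −15.5% | −30.4% |
| 0.3 SD | −2.3% | −10.2% | −24.2% |
| 0.6 SD | +1.5% | −4.5% | −17.1% |
| 1.0 SD | +6.8% | +4.7% | −4.8% |

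**Trigger.** The plan gives no threshold. With p < 0.05 and five independent variables (assumed), chance alone selects at least one in 1 − 0.95⁵ = 22.6% of trials. If the strata keep mood and substance use from triggering, it is 1 − 0.95³ = 14.3%.

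**Timing.** Table E-3 schedules COWS at baseline and 1 week, and craving, pain treatments and mood symptoms at baseline and at 1, 3 and 6 months. The H2 text specifies baseline measures. Neither says which visit's value enters the adjusted H1 or H3 models.

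**The case against.** The primary result is unharmed, and at the protocol's own rates nothing is lost. The power argument needs a smaller difference than 61% vs 24% and prognostic strengths that the documents do not give. Even then, what is forgone is a possible gain, since arm-only power does not fall below about 80% in the table. All of this stands. So does the point that only the primary logistic model is quantified; no figure is offered for retention, illicit-use days or pain. Against it, D.2.12 enlarges the sample precisely in case TAU uptake exceeds 24%, and smaller differences are where the strata help.

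Baseline substance use and mood symptoms can enter the additional analyses. They are related to the strata but are not the strata.

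The medication rule has narrow reach. Apart from its mediator role in H2, withdrawal is an outcome only in E1, and E1 as written omits the term. Nine of the twelve cells show attenuation; the three positive ones need a drug effect of at least 0.6 SD. What the documents show for certain is a mismatch between D.2.7 and E1. The distortion follows only if D.2.7 is applied.

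A reader might infer that covariate timing is stated nowhere. That goes too far: Table E-3 gives visits, sociodemographics are baseline only, one list says baseline substance use, and H2 refers to baseline measures. The gap is limited to the visit used in the adjusted H1 and H3 models.

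**Conclusion.** The point holds as a specification gap that should be closed before analysis. Randomisation is stratified by three factors that the primary model and the H1 and H3 mixed models do not name, and the arm-difference trigger would not be expected to supply them. Under the assumed 61% vs 44% uptake and three equally prognostic factors, the forgone gain is about 1 to 2 points of power at OR 1.5 to 2 and 4 to 5 points at OR 3. Type I error is then about 3 to 4% at OR 2 to 3.

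A reader might infer that the primary estimate is biased, that false positives are inflated or that the sample size is wrong. The documents support none of these: randomisation protects the arm comparison, the omission errs on the conservative side, and 27 per arm reproduces.

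The medication rule conflicts with E1 and, if followed, distorts the arm comparison of withdrawal, mostly towards attenuation (about -30% to +7% under assumed inputs). It does not touch the uptake outcome.

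**What to change.** - Add the three stratification factors to the primary logistic regression and to the H1 and H3 models. Report a standardised risk difference beside the odds ratio, because the odds ratio becomes conditional.
- Remove adjunctive medication as a covariate from withdrawal models that estimate the arm effect. Report its use by arm, and make D.2.7 and E1 agree.
- In the additional H1 and H3 analyses, replace the reference back to earlier variables and the arm-difference trigger with a named, pre-specified set of pre-randomisation covariates. Leave post-randomisation variables to H2 and H4.

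The cost is SAP wording. The strata are recorded for randomisation, and baseline values are already collected under Table E-3. No sample size, visit or clinical procedure changes.
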